10.4.4 WS2: Qualitative work

[name] will lead this WS and oversee a research assistant who will conduct the data collection and analysis.

10.4.4.1 Rationale

This WS complements the other WSs to investigate and understand the practicalities of implementing the PenA de-labelling intervention. As stated previously, the evidence base is under-developed in this area and our approach draws on qualitative research methods including semi-structured interviews and focus groups^{39,40} to explore the diverse perspectives that may influence the development and implementation of the intervention and associated pathway.

10.4.4.2 Aim

To identify the individual and organisational factors that may influence implementation and adoption of the PenA de-labelling intervention.

10.4.4.3 Objectives

- I. To gain the individual practitioner and patient perspectives on DPC.
- II. To determine potential enablers and barriers for their willingness to undertake or implement DPC.
- III. To establish the contextual factors, processes and infrastructure that may influence the implementation and sustainability of the intervention.

10.4.4.4_Methods

Semi-structured interviews and focus groups will be used to collect data on the behavioural insights and changes that may be required for the de-labelling intervention to be fully implemented.

Participants and sampling strategy:

Our target population is key stakeholders including patients, HCPs, operational managers, and commissioners who may influence individual or organisational factors implicated in the changes required for adoption of the new pathway. Inclusion criteria for participants will incorporate diversity in terms of gender, age and other characteristics. Patient interviews will begin at week 8 after WS1 to allow a period of set up and familiarisation and will be conducted at regular intervals as the intervention is introduced and embedded within the sites. Focus groups will be conducted midway through WS1 to allow a period of embedding.

a) Patients

Patients will be invited to participate in this WS at the time of recruitment for WS1 through WS1 coresearch staff at each site and followed up by WS2 research staff to confirm participation and consent. Details including patients study identification number, email id and telephone number will be securely transmitted by WS1 research staff to WS2 research staff. The WS2 staff will delete email id and telephone numbers from their records after the interview has been completed (and email the patient to confirm accordingly).

An equal number of 'low risk' patients who have completed a DPC and those who declined the DPC will be invited for interview. Interviews will be conducted either face-to-face, or *via* virtual platforms or telephone. One-to-one semi-structured interviews will be conducted with patients using an interview schedule designed according to the aims and objectives stated above (Appendix-11.10). Interviews will explore individuals' understanding, willingness and experience regarding DPC. The interview questions will be informed by risk perception theories⁴¹ and developed from relevant literature and the experience of the research team. The interview schedule will mainly comprise open questions to allow patients to provide their own perspectives, be iterated in consultation with our patient and public partners and piloted before use to ensure face validity.

We anticipate a total of 10-15 interviews at each site, although this will be subject to saturation checking⁴⁴. Through targeted patient recruitment we will ensure, as far as possible, that the interview sample reflects diversity with respect to gender, age, ethnicity and any other characteristics identified as important during the data collection period.

b) Other stakeholders

We will convene focus groups (in person or online) with other stakeholders to gather collectively refined accounts of the wider behaviours and contexts affected by the proposed intervention⁴². We will purposively sample prescribers, pharmacists, nurses, microbiologists, allergy specialists, operational

and business managers, clinical leaders and commissioners for inclusion within each site. The relevant personnel will be invited to participate *via* internal emails from local PI as well as posters advertising the study in relevant clinical and non-clinical areas. A list of those interested in participating from different professional groups will be drawn up by the local PI and shared with the WS2 team in a secure fashion. [name] will lead on selecting a sample of healthcare workers which best represents the widest range of views. Participants will sign an informed consent prior and this process will be coordinated by WS1 coordinator at respective sites. As data collection proceeds and we become aware of gaps in our knowledge, we may request that some participants snowball invitations to relevant colleagues. This process will be managed by the research team to ensure that we achieve our objectives.

Two members of the research team will facilitate the discussions using a topic guide and stimulus material relating to de-labelling will be used to prompt discussion. The focus group topic guide (Appendix-11.11 for topic guide, Appendix-11.12 for participant information sheet, Appendix-11.13 for Focus Group Consent Form) informed by relevant domains of the Theoretical Domains Framework⁴³, will enable discussion of participant views and perceptions regarding implementation of PenA delabelling in routine clinical care.

As contextual factors may play a role at each site, we anticipate conducting at least one focus group per site, each comprising 8-10 participants (up to a total of 3 focus groups).

We will observe good research ethics conduct at each stage of recruitment and data collection.

10.4.4.5 Data collection and processing

Interviews will be arranged and conducted either whilst the patient is still in hospital or soon after discharge. Interviews will be conducted face-to-face (with appropriate COVID-19 precautions) or *via* telephone or virtual platform depending on patient preference. With the consent of the patient, interviews will be audio recorded, anonymised by the researcher and then transcribed verbatim by a professional transcribing service as soon as possible after conducting the interviews.

Focus groups will be held on each site to maximise participation, and we anticipate that they will last between 90 and 120 minutes. Focus group participants will be asked to fill in a short questionnaire on socio-demographic data and sign a consent form (Appendix –11.13) before the start of the focus groups. Focus groups will also be audio recorded and transcribed verbatim by a professional transcribing service.

All qualitative data will be entered into NVivo software (QSR International (UK) Limited, Southport, UK), a data management and analysis programme to enable the application of qualitative analytical procedures which employ a system of coding and memoing developed by Lofland and Lofland (1995).

10.4.4.6 Analysis

A full descriptive analysis will be conducted to meet study objectives. Interviews and focus group transcripts will be analysed using thematic coding mapped to the theoretical domains framework to understand the cognitive, affective, social, environmental, organisational and professional influences on behaviours relating to PenA status de-labelling. The WS2 researcher will code emerging themes drawing on the theoretical frameworks that underpin the interview schedule and topic guide. An iterative approach using constant comparison will be employed in the development of coding frames and coding of data. A second WS2 researcher will read all the transcripts and code a sample to ensure reliability. Emerging themes will be discussed at team meetings and shared with our patient representatives to confirm that interpretations made by researchers stay close to the direct experience of patients.

Data handling: We will preserve participant confidentiality in accordance with the Data Protection Act 2018 and the General Data Protection Regulations 2018. Patients and stakeholders participating in WS2 will be assigned a unique identifier and all data will be anonymised and stored securely on University College London Hospitals (UCLH) NHS Foundation Trust premises using a secure drive to which immediate members of the project team will have access. Interviews and focus groups will be recorded using encrypted recording devices, with audio files securely stored on UCLH NHS Foundation Trust network servers. Transcription will be conducted by an institution-approved company, subject to a confidentiality agreement. Transcripts will be password-protected and stored on UCLH NHS Foundation Trust network servers. Consent forms will be stored in locked cabinets in a secure office within UCLH NHS Foundation Trust. In accordance with UCLH NHS Foundation Trust regulations, we will retain the anonymised research data for ten years in secure archives on UCLH NHS Foundation Trust premises, with [name] as data custodian. At the end of the study, with participants' consent, data in the form of anonymised transcribed interviews will be stored in the [sponsor site – University Hospitals Birmingham NHS Foundation Trust] data repository and will be made available to bona fide researchers on request.

Outputs: This WS will generate insights into factors relating to organisational context, treatment pathway, protocol implementation, time taken and resources and contribute to understanding of the influences on patient and HCP behaviours, and perspectives of managerial and operational stakeholders in organisations. The findings will contribute to our 'stop/go' criteria (see 4.6).

10.4.5 WS3: Health Economic Modelling

[name] will lead this workstream and will be supported by a research fellow undertaking data collection and analysis.

Care pathway mapping: A care pathway mapping exercise (month 1), including the academic study team and clinical representatives from the three study sites will be conducted to fully map the respective clinical pathways for the proposed PenA de-labelling programme and current practice. Anticipated decision points where patient management will change and potentially impact on patient health will be identified, in addition to expected resource use required to deliver each aspect of the pathways. Differences in local management will be identified and consensus will be met on the pathway that will form the base case analysis and any regional differences that should be explored in scenario analyses.

Development of model structure and identification of model parameters: The comparative pathways mapped will inform the structure of the decision-analytic model and facilitate identification of the data required to parameterise the model (months 1-3). This information will be fed back to the wider study team to ensure that the necessary data are collected from study participants and local project managers.

Construction of decision-analytic model: A study team meeting (month 18) will be convened to represent the decision-analytic model structure and explore whether the results from WS 1 and 2 have led to any changes to the proposed PenA de-labelling programme or highlighted any additional scenarios that we need to explore in the economic modelling. The model will then be constructed (months 18-24) in line with the International Society for Pharmacoeconomics and Outcomes Research (ISPOR) good practice recommendations⁴⁵. The model will compare the cost-effectiveness of the proposed PenA de-labelling programme with current practice. The model will conceptualise patients passing through the pathway and allow estimation of the potential impact of introducing the PenA delabelling programme on patient health and costs. Data from the study will be used to inform model parameters, including but not limited to patient characteristics, proportion stratified into 'low risk' and 'high risk' groups and DPC outcomes. A NHS and personal and social services perspective will be adopted, in line with NICE recommendations. Key model outcomes will include incremental costeffectiveness ratios (ICERs) and net health benefit. Probabilistic analysis will be used to account for and describe uncertainty in model parameter estimates. Scenario analyses will be conducted to help understand the impact of any assumptions made or regional differences in patient management previously identified.

Value of information analysis: Based on our decision-analytic model, we will use value of information analysis⁴⁶ to estimate the expected value of perfect information (EVPI) which can be used to guide whether it is of value to collect further data to reduce the probability of making the 'wrong' decision. We will also calculate the expected value of perfect parameter information (EVPPI) which estimates the value of removing uncertainty in specific model parameters. These analyses will be used to help determine whether further research is needed and also guide future study designs.

Engagement with service managers: The results of the economic modelling will be presented to service managers at each of the 3 study sites to explore their perspective on the economic viability of the proposed PenA de-labelling programme and to ascertain what, if any, further evidence they would require to adopt the programme at their hospital.

10.4.6 'Stop/Go' criteria

A traffic light system will be followed to determine a staged roll out of the intervention in the NHS as per following metrics:

(Red – 'stop', Amber – 'review protocol by study steering group' and Green – 'Go').

- 1. Complete study documentation: >80% Green; ≥70-80% Amber; <70% Red.
- 2. Completed DPCs amongst recruited participants: >65% Green; 50-65% Amber; <50% Red.
- 3. 0% DPCs cause serious reactions Green.
- 4. Conclusions from qualitative research are in support of this approach Green.
- 5. Other scenarios 'Amber':
 - a. DPCs cause serious reactions (i.e., serious cardio-respiratory compromise necessitating admission in intensive care unit, SJS, TEN, DRESS) each adverse clinical outcome will be carefully reviewed and interpreted with respect to its timing, clinical context, severity, nature of index episode and patient feedback/perception. Based on our findings, inclusion and exclusion criteria and protocol for DPC will be amended by the investigators as deemed necessary either during the study or following its completion. Further external input from international experts or those from British Society for Allergy and Clinical Immunology (BSACI) will be sought if needed.
 - b. Any concerns emerging from patients, HCPs and managers will be carefully considered and treatment pathways and governance framework ratified by the study steering group.

10.4.7 Sample size calculation

Sample size calculation for DPCs: A recent systematic review (OP-JACR200125 1..10 (nih.gov) involving 1202 patients in 13 studies (inpatient and outpatient 'low risk' PenA cohorts) reported ~97% de-labelling and there were no severe adverse reactions related to DPC. To estimate this rate with a

95% confidence interval (±3%), a total number of at least 122 DPCs are required across the 3 participating sites.

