10.2.3 Review of evidence

This topic has been reviewed by the applicants¹⁻⁴ and others^{14,16}. This multidisciplinary approach is underpinned by a relatively simple guideline-based risk stratification process^{1,6,14}. Alongside, there is a need for a validated treatment pathway supported by an appropriate governance framework.

Our preliminary work and recent evidence from USA, Australia and New Zealand have shown that multidisciplinary PenA de-labelling pathways employing a risk stratification process including a DPC is a promising approach to improve antimicrobial stewardship and reduce healthcare costs^{6,30-32}. However, there are some gaps in our understanding in some highly relevant areas relating to this model. Further insight is required into the following:

- (a) behaviour/perceptions of patients/HCPs in secondary care regarding this approach
- (b) time and resource required to support the process
- (c) views of senior management in secondary care

This knowledge will be crucial in delineating treatment pathways and governance frameworks.

We reported a high negative predictive value (94%) for a risk stratification algorithm in accurately identifying 'low risk' patients with PenA⁹. We also safely de-labelled 54 patients in a pre-operative

surgical setting and received positive patient feedback regarding DPC⁶. The risk stratification process was carried out by trained staff nurses and overseen by an anaesthetist with expertise in PenA delabelling. Another study from New Zealand reported safety of a similar approach in an inpatient setting with risk stratification performed by trained pharmacists³⁰. Blumenthal et al. employed a similar model in Harvard group of hospitals on the medical wards and reported its safety and enhanced prescription rates for penicillins and other betalactam antibiotics by 7-fold³³. The projected cost saving was \$8.3-13.4m USD *per annum* in the Harvard group of hospitals¹⁶. Similarly, the lead applicant's group reported that their Trust incurred between £250-500k annually for alternative antibiotics in PenA labelled patients¹⁰. The applicants have published a narrative review² of recent studies^{6,30,31,33-35} attesting to the safety of a DPC in 'low risk' patients.

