- 4. Time taken to complete screening log and risk stratification proforma.
- 5. Overall proportion stratified as 'low risk' and high risk'.
- 6. Overall proportion of 'low risk' that agreed to undergo DPC.
- 7. Overall proportion of patients declining to undergo DPC.
- 8. Proportion of those stratified as 'high risk' and 'low risk' (those declining DPC) meeting national criteria¹⁸ for referral to an allergy specialist for PenA skin tests.
- 9. Outcome of DPCs:
 - a. Proportion successfully de-labelled.
 - b. Description of adverse reactions (immunological or nonimmunological).
 - c. Proportion of patients that did not complete DPC with description (eg: those that undergo first dose of DPC and then opt out of the study).
 - d. Proportion of 'dropouts' with description (eg: those that express interest and default appointment at DPC).
 - e. Proportion of immediate (including severity as per international grading system^{37,38}) and nonimmediate HSRs (descriptive analysis) and other adverse reactions and treatment received.

*Descriptive data regarding inter-site and inter-clinical setting will be summarised as N=(%)

Patient pathways for WS1 are summarised in Appendices 11.08 and 11.09.

A total number of 122 DPCs will be conducted across the 3 participating centres in the above clinical settings. In the event that the recruitment targets are not met at an individual centre, other centres will aim to compensate with additional participants to achieve the proposed number of DPCs.

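### The 122 DPCs reproduce under the usual formula, but the ±3% is not a 95% precision on the lower side: near 97% a valid interval reaches down to about 92–93%, not 94%

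*Protocol*

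**What the plan says.** Protocol section 10.4.7 rests the number of direct oral penicillin challenges (DPCs) on a systematic review "involving 1202 patients in 13 studies", which "reported ~97% de-labelling and there were no severe adverse reactions related to DPC". It then sets the precision and the size: "95% confidence interval (±3%), a total number of at least 122 DPCs are required across the 3 participating sites". No interval method is named.

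Section 10.4.3.3 repeats the target: "A total number of 122 DPCs will be conducted across the 3 participating centres in the above clinical settings". The matching output, in the list of DPC outcomes in the same section, is "Proportion successfully de-labelled". Section 10.3.3 places the proportion of low-risk patients who get through the challenge safely among the secondary outcomes.

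**The concern.** A symmetric ±3 points around 97% runs from 94% to 100%. That shape is typical of the normal approximation, which behaves badly when the proportion is close to 1 and few failures are expected. If so, the printed half-width does not carry the 95% confidence attached to it, and the shortfall falls on the lower limit.

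The lower limit matters most for a de-labelling programme, because it bounds how often a challenge fails to remove the label. A reader of section 10.4.7 would expect an on-target result to exclude rates below about 94%, that is, failure rates above about 6%. DPC outcomes also feed the economic model in section 10.4.5, whose probabilistic analysis is meant to describe parameter uncertainty. This is the only numerical justification given for the number of challenges, so the precision it promises should be one the study can deliver.

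**Working it through.** **Inputs.** Anticipated rate p ≈ 0.97, precision d = 0.03, confidence 95% (taken as two-sided, z = 1.96) and n = 122, all from section 10.4.7.

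**Step 1: reproduce the plan's figure.** Wald precision formula: n = z² p(1 − p) / d².
- At p = 0.97: 1.96² × 0.97 × 0.03 / 0.03² = 124.2.
- At p = 0.9706: 1.96² × 0.9706 × 0.0294 / 0.03² = 121.8, which rounds up to 122. A rate of 97.06% still reads as about 97%.
- Wald half-width at n = 122, p = 0.97: 1.96 × √(0.97 × 0.03 / 122) = 0.0303, or 3.03 points.

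So 122 and ±3% are consistent with each other under this formula.

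**Step 2: does that interval have 95% coverage?** Expected failures are 122 × 0.03 = 3.7. Exact coverage is the sum of the binomial(122, 0.97) probabilities of the results whose interval contains 97%:

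| Interval | Coverage at true 97%, n = 122 |
|---|---|
| Wald | 88.0% |
| Wilson | 96.9% |
| Clopper-Pearson | 96.4% |

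Most of the Wald shortfall comes from results of 121/122 and 122/122, with probabilities 9.2% and 2.4%. Their Wald intervals (97.6–100% and 100–100%) lie wholly above 97%, so the lower limit is too high.

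**Step 3: intervals near the target.** The two results either side of 97% are 118/122 (96.7%) and 119/122 (97.5%). The latter is the most likely single result at a true 97%.

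| Result | Method | 95% interval | Points down / up | Mean half-width |
|---|---|---|---|---|
| 118/122 | Wald | 93.6–99.9% | 3.2 / 3.2 | 3.2 |
| 118/122 | Wilson | 91.9–98.7% | 4.9 / 2.0 | 3.4 |
| 118/122 | Clopper-Pearson | 91.8–99.1% | 4.9 / 2.4 | 3.6 |
| 118/122 | Jeffreys | 92.4–98.9% | 4.3 / 2.2 | 3.2 |
| 119/122 | Wilson | 93.0–99.2% | 4.5 / 1.6 | 3.1 |
| 119/122 | Clopper-Pearson | 93.0–99.5% | 4.6 / 2.0 | 3.3 |

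Evaluated at exactly 97%, Wilson gives 92.3–98.9% and Clopper-Pearson 92.2–99.2%.

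**Step 4: how often would the lower limit reach 94%?** By Wilson or Clopper-Pearson this needs at least 120/122, where the lower limit is 94.2%. At a true 97% the probability is 17.2% + 9.2% + 2.4% = 28.8%, a little under three in ten.

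**The case against.** The best defence is that ±3% is only a planning half-width. The protocol does not commit to a Wald analysis, and the choice of interval is commonly left to the statistical analysis plan. The 88% coverage would then describe an analysis nobody has specified. The loss is also one-sided: averaged over both arms, the half-width at 118/122 is 3.4 (Wilson) to 3.6 (Clopper-Pearson) points, about half a point more than stated. The outcome is secondary, no hypothesis is tested, and none of the stop/go metrics in section 10.4.6 uses a de-labelling threshold.

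Much of this stands, and it limits the importance of the point. It does not rescue the wording. The objection here is not that a method is missing. The protocol states a numerical 95% precision, and none of the Wilson, Clopper-Pearson or Jeffreys intervals delivers its lower arm with 122 challenges and about 97% success.

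Four stronger readings are tempting, and the document does not support them:
- **That 122 is a miscalculation and should be 125.** The input is rounded, and 97.06% gives 122.
- **That the protocol contradicts its own evidence.** Section 10.2.3 says "We reported a high negative predictive value (94%) for a risk stratification algorithm", but that is a predictive value from the investigators' earlier work. It is not offered as the design rate and does not conflict with a de-labelling rate from a review of low-risk cohorts. Putting 94% into the Wald formula would also reuse the approximation criticised here.
- **That the overall rate will be reported without an interval.** The sentence "Descriptive data regarding inter-site and inter-clinical setting will be summarised as N" (and percentage) concerns comparisons between sites and settings, not the overall proportion.
- **That the study is too small.** About 241 (Wilson) to 244 (Clopper-Pearson) challenges would be needed for a lower arm of 3 points at 97%, but the protocol sets no such one-sided target.

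**Conclusion.** The point holds as a misstatement of precision, not as an error in the sample size. The figure of 122 is consistent with about 97% ±3% under the Wald formula. At that rate and size the formula's interval has about 88% coverage, and intervals with coverage close to 95% have a lower limit of about 92–93% rather than 94%. The upper side is tighter than stated, so the total width is only slightly larger than implied.

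This assumes a true or observed rate near 97%, all 122 challenges in the denominator, and independent binomial outcomes. The consequence is modest because the outcome is secondary and descriptive. The correction is still worth making, since it costs almost nothing and concerns the limit that readers will use.

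**What to change.** Keep 122 DPCs. In section 10.4.7 replace the ±3% statement with wording such as: '122 DPCs give an expected 95% Wilson (or Clopper-Pearson) interval of about 92% to 99% if about 97% are de-labelled.' Choose one of the two methods and report that interval for the overall de-labelling proportion in the Workstream 1 outputs of section 10.4.3.3.

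Optionally, add one lower rate as a sensitivity value, labelled as such and not as the design rate. At 94% the Clopper-Pearson interval with 122 challenges is about 88% to 97.5%.

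The cost is a wording amendment and a slightly less favourable precision statement. No extra participants, procedures or data are needed.
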